**Table 3 PP Set Exclusion Criteria for Dosing Errors**

Group Name	Exclusion Conditions
mRNA-1273 CCI + placebo	Any mRNA-1010 received or mRNA-1073 received or mRNA-1273 received CCI or mRNA-1273 received CCI
mRNA-1010 CCI + placebo	Any mRNA-1273 received or mRNA-1073 received or mRNA-1010 received CCI or mRNA-1010 received CCI
mRNA-1010 CCI + mRNA-1273 CCI co-administration	Any mRNA-1073 received or mRNA-1010 received CCI CCI or mRNA-1010 received CCI or mRNA-1273 received CCI or mRNA-1273 received CCI
mRNA-1073 CCI + placebo	Any mRNA-1273 received or mRNA-1010 received or mRNA-1073 received CCI or mRNA-1073 received CCI
mRNA-1073 CCI + placebo	Any mRNA-1273 received or mRNA-1010 received or mRNA-1073 received CCI or mRNA-1073 received CCI
mRNA-1073 CCI + placebo	Any mRNA-1273 received or mRNA-1010 received or mRNA-1073 received CCI or mRNA-1073 received CCI

Note: ‘≤ x.x µg’ includes the missing injection (i.e. 0.0 µg) of the planned vaccination.

#### 5.4. Safety Set

The safety set consists of all randomly assigned participants who receive the IP. The safety set will be used for all analyses of safety, except for the solicited ARs. Participants will be included in the vaccination group corresponding to what they actually received according to the rules given below in Table 4:

**Table 4 Vaccination Group Corresponding to Dose Received**

Group Name	Conditions
mRNA-1273 CCI + placebo	No mRNA-1010 received and No mRNA-1073 received and mRNA-1273 dose CCI
mRNA-1010 CCI + placebo	No mRNA-1273 received and No mRNA-1073 received and mRNA-1010 dose CCI
mRNA-1010 CCI + mRNA-1273 CCI co-administration	No mRNA-1073 received and mRNA-1273 dose CCI and mRNA-1010 dose CCI
mRNA-1073 CCI + placebo	No mRNA-1010 received and No mRNA-1273 received and mRNA-1073 dose CCI
mRNA-1073 CCI + placebo	No mRNA-1010 received and No mRNA-1273 received and mRNA-1073 received CCI and mRNA-1073 received CCI
mRNA-1073 CCI + placebo	No mRNA-1010 received and No mRNA-1273 received and mRNA-1073 received CCI and mRNA-1073 received CCI

## 5.5. Solicited Safety Set

The solicited safety set consists of all participants in the safety set who contribute any solicited AR data. The solicited safety set will be used for the analyses of solicited ARs and participants will be included in the vaccination group corresponding to what they actually received.

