## 3. Study Endpoints

### 3.1. Primary Endpoints

The primary objective will be evaluated by the following endpoints:

- Frequency and grade of each solicited local and systemic reactogenicity AR during a 7-day follow-up period post vaccination
- Frequency and severity of any unsolicited adverse events (AEs) during the 28-day follow-up period post vaccination
- Frequency of any serious adverse events (SAEs), adverse events of special interest (AESIs), medically attended adverse events (MAAEs), and AEs leading to discontinuation from Day 1 to Day 181/EoS

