## 6. Statistical Analysis

### 6.1. General Considerations

All analyses will be conducted using SAS Version 9.4 or higher. Statistical outputs (tables, figures, listings, and datasets) will refer study participants as subjects and will use injection of IP and injection interchangeably.

**Continuous variables** will be summarized using the following descriptive summary statistics: the number of subjects (n), mean, standard deviation (SD), median, minimum (min), and maximum (max).

**Categorical variables** will be summarized using counts and percentages.

**Baseline value**, unless specified otherwise, is defined as the most recent non-missing measurement (scheduled or unscheduled) collected before the dose of IP in this study. For immunogenicity tests and nasopharyngeal (NP) swab tests, the baseline is defined as the most recent non-missing result/measurement (scheduled or unscheduled) collected before or on the date (and time, if available) of injection (Day 1).

For the summary statistics of all numerical variables unless otherwise specified, the display precision will follow programming standards. Please see [Appendix A](#) for variable display standards.

When count data are presented, the percentage will be suppressed when the count is zero in order to draw attention to the non-zero counts. A row denoted “Missing” will be included in count tabulations where specified on the shells to account for dropouts and missing values. The denominator for all percentages will be the number of subjects in the treatment group within the analysis set of interest, unless otherwise specified.

Symptomatic COVID-19 is defined by the presence of one of the CDC-listed symptoms (CDC [2021c](#)) and a positive RT-PCR test on a respiratory sample.

Asymptomatic SARS-CoV-2 infection is defined as a positive RT-PCR test on a respiratory sample in the absence of symptoms or a positive serologic test for anti-nucleocapsid antibody after a negative test result at the time of enrollment, with the serologic assay detecting previously resolved SARS-CoV-2 infections that may have occurred between visits, and the RT-PCR to detect active viral infection at the time of a visit.

The following analysis periods of safety analyses will be used:

- Overall period: from the day of vaccination (Day 1) and continues through the earliest date of (study completion, discontinuation from the study, or death).

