**Incomplete/missing data:**

- Imputation rules for missing prior/concomitant medications, non-study vaccinations and procedures are provided in [Appendix C](#).
- Imputation rules for missing AE dates are provided in [Appendix D](#).
- If antibody values reported as below the LLOQ (e.g.,  $<0.1$ ), the numeric values will be imputed by  $0.5 \times \text{LLOQ}$  in the summary. If antibody values reported as greater than the ULOQ (e.g.,  $>3000$ ), the numeric values will be imputed by ULOQ in the summary if actual values are not available.
- Other incomplete/missing data will not be imputed, unless specified otherwise.

**Table layouts** will be presented according to vaccination group and, separately, randomization stratification factors.

The following vaccination groups will be used for summary purposes:

- mRNA-1273 **CCI**+ placebo
- mRNA-1010 **CCI**+ placebo
- mRNA-1010 **CCI**+ mRNA-1273 **CCI** co-administration
- mRNA-1073 **CCI**+ placebo
- mRNA-1073 **CCI**+ placebo
- mRNA-1073 **CCI**+ placebo
- All (the combined group will be applicable to the disposition and baseline demographic only)

As well, the following groups will be used for summary purposes:

- Overall
- Age: 18 to 49 years old
- Age: 50 to 75 years old

All analyses will be conducted using SAS Version 9.4 or higher.

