### 6.4.1. Solicited Adverse Reactions

An AR is any AE for which there is a reasonable possibility that the test product caused the AE. The term “Solicited Adverse Reactions” refers to selected signs and symptoms occurring after injection administration during a specified post-injection follow-up period (day of injection and 6 subsequent days). An eDiary will solicit daily the participant on the occurrence and intensity of selected signs and symptoms using a pre-defined structured checklist.

The following local ARs will be solicited by the eDiary: injection site pain, injection site erythema (redness), injection site swelling/induration (hardness), and underarm gland swelling or tenderness.

The following systemic ARs will be solicited by the eDiary: headache, fatigue, myalgia (muscle aches all over the body), arthralgia (aches in several joints), nausea/vomiting, chills, and fever.

The solicited ARs will be graded based on the grading scales presented in Table 6 in the protocol, modified from the Toxicity Grading Scale for Healthy Adult and Adolescent Volunteers Enrolled in Preventative Vaccine Clinical Trials ([DHHS 2007](#)).

If a solicited local or systemic AR continues beyond 7 days post-injection, the subject will be prompted to capture solicited local or systemic AR in the eDiary until resolution, not to exceed 28 days after study injection.

All solicited ARs (local and systemic) will be considered causally related to dosing.

Analyses of solicited ARs will be provided by vaccination group based on the Solicited Safety Set. Summaries of local solicited ARs will be also presented by vaccination group and injection content received in the corresponding side/deltoid.

The number and percentage of participants with any solicited local ARs, solicited systemic ARs, and solicited ARs during the 7-day follow-up period after the injection will be summarized, along with the number of events under each category. A two-sided 95% exact CI using the Clopper-Pearson method will be provided for the percentage of participants who reported any solicited local AR, solicited systemic AR, or any solicited AR.

The number and percentage of participants who reported each individual solicited local AR and solicited systemic AR during the 7-day follow-up period after injection will be provided by severity grade.

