The number and percentage of subjects experiencing fever (a temperature greater than or equal to 38°C/100.0°F by the oral route) by severity grade and the number and percentage of subjects experiencing a fever of Grade 3 or higher temperature (a temperature greater than or equal to 39.0°C/102.1°F by the oral route) will be provided.

The onset of individual solicited AR is defined as the time point after injection at which the respective solicited AR first occurred. The number and percentage of subjects with onset of individual solicited AR will be summarized by study day relative to the injection (Day 1 through Day 7). The day of onset of each solicited AR within 7 Days will be summarized.

The duration of local or systemic solicited ARs, along with the specific individual solicited ARs, will be calculated as: reaction end date – reaction start date +1, no matter it is intermittent or continued or if the solicited AR continues beyond 7 days. The duration of each solicited AR within 7 Days will be summarized.

All solicited ARs that continue beyond 7 days post-injection will be summarized.

All delayed ARs with onset day after 7 days post injection will also be summarized.

These summaries may be provided for additional subgroups of selected baseline characteristics.

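### Every member of the Solicited Safety Set stays in the denominator of every 7-day reaction percentage, so a wholly unanswered item acts as no reaction and can only lower the reported rate

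*SAP*

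**What the plan says.** The first primary endpoint (SAP Section 3.1) is "Frequency and grade of each solicited local and systemic reactogenicity AR during a 7-day follow-up period post vaccination".

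Four statements in the SAP determine how its percentages are formed:

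- **Set (Section 5.5):** "The solicited safety set consists of all participants in the safety set who contribute any solicited AR data". There is no minimum number of items or days, and no limit to Days 1–7.
- **Analysis (Section 6.4.1):** "Analyses of solicited ARs will be provided by vaccination group based on the Solicited Safety Set". The planned output is "The number and percentage of participants who reported each individual solicited local AR and solicited systemic AR during the 7-day follow-up period", split by grade. The section lists 4 local and 7 systemic reactions, 11 in all. Exact Clopper-Pearson intervals are planned for three summary lines only: any local, any systemic and any solicited reaction.
- **Denominator (Section 6.1):** "The denominator for all percentages will be the number of subjects in the treatment group within the analysis set of interest, unless otherwise specified".
- **Missing data (Section 6.1):** "Other incomplete/missing data will not be imputed, unless specified otherwise". No rule deals with unanswered diary items. A row for missing values appears only where the table shells ask for one.

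Sections 5.5 and 6.4.1 name no other denominator, either per reaction or per category.

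**The concern.** Entry to the set is decided once, on any solicited-reaction data, but the set then serves as the denominator for 11 different items. A participant who completed the local items and never entered a temperature is in the set and counts towards the fever denominator, yet can never appear in the fever numerator. In the percentage, that participant cannot be told apart from someone who measured their temperature and had no fever.

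The study tests no hypotheses (Section 4.2), so these descriptive percentages are the primary result. An error that can only understate reactogenicity deserves attention in a safety endpoint. If completion happened to differ between vaccination groups, the same rule could also create or mask a difference between them.

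**Working it through.** **The plan's own figures.** Table 2 gives the chance of seeing at least one event as 1 − (1 − p)^n. For n = 50 this gives 92.3% at p = 5% and 78.2% at 3%. For n = 100 it gives 95.2% at 3% and 86.7% at 2%. All four match. They assume that every participant is fully observed. If a share m goes unrecorded, p becomes p(1 − m), and the last figure falls to 85.3%, 83.7% and 80.1% at m = 5%, 10% and 20%. That loss comes from the missing answers themselves, and no choice of denominator restores it. The denominator affects the reported percentage, as follows.

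**Inputs.** N = 100 per group (Table 1; the mRNA-1273 group has 50). The SAP gives no expected reaction rate and no diary completion rate, so both of these are assumptions:

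- p: true 7-day rate of a reaction among set members.
- m: share of set members with no recorded answer to that item in Days 1–7, taken as unrelated to whether the reaction occurred.

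**Formula.** The expected numerator is N·p·(1 − m).

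- SAP default: N·p·(1 − m) / N = p(1 − m), a shortfall of p × m.
- Item-level denominator: N·p·(1 − m) / [N(1 − m)] = p.

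If non-response is related to the reaction, the shortfall under the default is p times the unrecorded share among those who had the reaction. It is still never negative.

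**Shortfall in percentage points (100 × p × m):**

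| True rate p | m = 2% | m = 5% | m = 10% | m = 20% |
|---|---|---|---|---|
| 2% | 0.04 | 0.1 | 0.2 | 0.4 |
| 10% | 0.2 | 0.5 | 1.0 | 2.0 |
| 50% | 1.0 | 2.5 | 5.0 | 10.0 |
| 70% | 1.4 | 3.5 | 7.0 | 14.0 |

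**Worked example, N = 100, p = 70%, m = 10%.** Recorded reactions: 100 × 0.70 × 0.90 = 63. Members with an answer: 100 × 0.90 = 90. The Clopper-Pearson limits are the 2.5% quantile of Beta(x, n − x + 1) and the 97.5% quantile of Beta(x + 1, n − x).

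- SAP default: 63/100 = 63.0%, 95% CI 52.8 to 72.4.
- Item-level denominator: 63/90 = 70.0%, 95% CI 59.4 to 79.2.

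The plan would print such an interval only for the three summary lines. For a single reaction it serves here only to show scale.

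**Two groups with the same true rate of 70%.** With m = 2% in one and 10% in the other, the default reports 68.6% and 63.0%, an apparent difference of 0.70 × (0.10 − 0.02) = 5.6 points. Both values of m are assumptions.

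**The case against.** The strongest reply is that the SAP nowhere says an unanswered item counts as no reaction. It reports how many set members reported each reaction, which is a legitimate descriptive quantity and not an imputation, so there is no formal contradiction with the missing-data rule. The shells are not shown and may carry a row for missing values. It is true that the effect follows from a default and not from an explicit instruction. But a missing row would only display the gap; the percentage would still be taken over all set members.

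A reader might infer several stronger points that the SAP does not support:

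- **That any eDiary entry admits a participant.** Section 5.5 requires solicited-reaction data. A pain or fever medication entry (Section 6.2.4) or a respiratory-symptom report (Section 6.3) would not qualify.
- **That the endpoint is biased low as a matter of fact.** There is no shortfall if diaries are complete, if the blanks were true negatives, or if the reaction was recorded on another of the seven days. The endpoint is ever reported within 7 days, under daily prompting.
- **That groups will differ in completion.** Nothing in the SAP suggests this. The study is observer-blind, and every single-product group also receives placebo.
- **That all intervals use too large an n.** Intervals are planned for three summary lines only. For any solicited reaction, every set member has contributed some solicited data by definition, so the set is close to the natural denominator there.
- **That participants who answered on one day only are dealt with by a responder denominator.** They are not; they remain in it.

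**Conclusion.** The point holds in limited form. Sections 5.5, 6.1 and 6.4.1 together keep every set member in the denominator of every 7-day reaction percentage, including members who never answered that item in Days 1–7. Wholly unanswered items therefore act as negatives, and any resulting error in the first primary endpoint is downward.

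The size cannot be determined from the SAP. On the assumed range of m from 2% to 20%, it is below 0.5 points for a 2% reaction and 1 to 14 points for reactions at 50% to 70%; with complete diaries it is zero. Those figures rest on m being the wholly unrecorded share over all seven days, not general item missingness, and on non-response being unrelated to the reaction. The point is worth correcting because the default is a stated rule with a one-directional effect on a primary endpoint and the replacement is cheap. It does not show that the study's rates will be wrong.

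**What to change.** Leave the definition in Section 5.5 unchanged. Requiring a Day 1–7 response for entry could drop participants needed for the summaries of delayed reactions, of reactions continuing past Day 7, and of pain or fever medication beyond 7 days, some or all of which use this set.

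In Section 6.4.1, override the Section 6.1 default for the 7-day summaries:

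1. Base each reaction's percentage on set members with at least one non-missing Day 1–7 response to that reaction. For fever, this means at least one temperature or a reported fever.
2. Base the any local, any systemic and any solicited percentages, with their Clopper-Pearson intervals, on members with at least one Day 1–7 response in that category.
3. Show this n in each row.
4. Add a table of eDiary days completed (0 to 7) by vaccination group, because the new denominator does not resolve partly completed weeks.

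The cost is SAP wording and table shells, with no new data. Denominators will vary slightly between rows, and reported rates will be slightly higher. A responder denominator is itself unbiased only if non-response is unrelated to the reaction, which is a further reason for the completion table. The change should be settled before unblinding, so that the denominator is not chosen after results are seen.

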## 6. Statistical Analysis

### 6.1. General Considerations

All analyses will be conducted using SAS Version 9.4 or higher. Statistical outputs (tables, figures, listings, and datasets) will refer study participants as subjects and will use injection of IP and injection interchangeably.

**Continuous variables** will be summarized using the following descriptive summary statistics: the number of subjects (n), mean, standard deviation (SD), median, minimum (min), and maximum (max).

**Categorical variables** will be summarized using counts and percentages.

**Baseline value**, unless specified otherwise, is defined as the most recent non-missing measurement (scheduled or unscheduled) collected before the dose of IP in this study. For immunogenicity tests and nasopharyngeal (NP) swab tests, the baseline is defined as the most recent non-missing result/measurement (scheduled or unscheduled) collected before or on the date (and time, if available) of injection (Day 1).

For the summary statistics of all numerical variables unless otherwise specified, the display precision will follow programming standards. Please see [Appendix A](#) for variable display standards.

When count data are presented, the percentage will be suppressed when the count is zero in order to draw attention to the non-zero counts. A row denoted “Missing” will be included in count tabulations where specified on the shells to account for dropouts and missing values. The denominator for all percentages will be the number of subjects in the treatment group within the analysis set of interest, unless otherwise specified.

Symptomatic COVID-19 is defined by the presence of one of the CDC-listed symptoms (CDC [2021c](#)) and a positive RT-PCR test on a respiratory sample.

Asymptomatic SARS-CoV-2 infection is defined as a positive RT-PCR test on a respiratory sample in the absence of symptoms or a positive serologic test for anti-nucleocapsid antibody after a negative test result at the time of enrollment, with the serologic assay detecting previously resolved SARS-CoV-2 infections that may have occurred between visits, and the RT-PCR to detect active viral infection at the time of a visit.

The following analysis periods of safety analyses will be used:

- Overall period: from the day of vaccination (Day 1) and continues through the earliest date of (study completion, discontinuation from the study, or death).
- 7 days following vaccination: this period includes the day of vaccination and 6 subsequent days, or up to the study discontinuation or death, whichever comes earlier. This analysis period will be used for solicited local and systemic AR that occur during this time.
- Up to 28 days following vaccination: starts from the day of vaccination (Day 1) and spans 28 days to include the day of vaccination and 27 subsequent days, or up to the study discontinuation or death, whichever comes earlier. This analysis period

will be used as the primary analysis period for safety analyses including unsolicited AE, except for solicited AR, unless specified otherwise.

**Study day relative to the injection** will be calculated as below:

- a) study day prior to the injection will be calculated as: date of assessment/event – date of the injection;
- b) study day on or after the date of the injection will be calculated as: date of assessment/event – date of the injection + 1;

**For calculation regarding antibody levels/titers**, antibody values reported as below the lower limit of quantification (LLOQ) will be replaced by  $0.5 \times \text{LLOQ}$ . Values that are greater than the upper limit of quantification (ULOQ) will be converted to the ULOQ if actual values are not available. Missing results will not be imputed.

**Unscheduled visits:** Unscheduled visit measurements will be included in the analyses as follows:

- In scheduled visit windows per specified visit windowing rules.
- In the derivation of baseline/last on-treatment measurements.
- In the derivation of maximum/minimum on-treatment values and maximum/minimum change from baseline values for safety analyses.
- In individual subject data listings.

**Visit window rules:** The analysis visit windows for protocol-defined visits are provided in [Appendix B](#).

**Incomplete/missing data:**

- Imputation rules for missing prior/concomitant medications, non-study vaccinations and procedures are provided in [Appendix C](#).
- Imputation rules for missing AE dates are provided in [Appendix D](#).
- If antibody values reported as below the LLOQ (e.g.,  $<0.1$ ), the numeric values will be imputed by  $0.5 \times \text{LLOQ}$  in the summary. If antibody values reported as greater than the ULOQ (e.g.,  $>3000$ ), the numeric values will be imputed by ULOQ in the summary if actual values are not available.
- Other incomplete/missing data will not be imputed, unless specified otherwise.

**Table layouts** will be presented according to vaccination group and, separately, randomization stratification factors.

The following vaccination groups will be used for summary purposes:

- mRNA-1273 **CCI**+ placebo
- mRNA-1010 **CCI**+ placebo
- mRNA-1010 **CCI**+ mRNA-1273 **CCI** co-administration
- mRNA-1073 **CCI**+ placebo
- mRNA-1073 **CCI**+ placebo
- mRNA-1073 **CCI**+ placebo
- All (the combined group will be applicable to the disposition and baseline demographic only)

As well, the following groups will be used for summary purposes:

- Overall
- Age: 18 to 49 years old
- Age: 50 to 75 years old

All analyses will be conducted using SAS Version 9.4 or higher.

